6.5 Other Monitoring During and After Intervention

The total volume of fluids received and total urine output will be recorded on a daily basis (24 hour summary) from the time of randomization through the first 5 days (through the end of the intervention period).

Concomitant medications administered from the time of randomization through Day 7 will be recorded. Selected procedures and therapies, including new tracheostomies and placement of chronic feeding tubes will be recorded from the time of randomization through hospital discharge.

After the 120 hour intervention period, no study-specific interventions will occur as part of the THAPCA Trials. At the discretion of the clinical care team, the arterial line, the central line, and all probes for temperature monitoring may be discontinued when no longer needed for clinical care.

Temperature management after the intervention period will be according to the usual PICU clinical practice at each site. The minimum and maximum daily temperatures, including the measurement site, will be recorded through day 10.

The date of each study subject's PICU discharge and hospital discharge will be recorded. Assessments of neurological and functional status will be obtained within 72 hours prior to hospital discharge, and at three and 12 months post arrest. The three month follow up is intended to help with subject retention by maintaining contact with the family, as well as helping us to test our primary endpoint conclusions for robustness with respect to missing data. See [Section 6.6 on the next page](#) for a detailed description of neurological and neurobehavioral outcomes, and a schedule of assessments.

6.6 Neurologic and Neurobehavioral Outcomes

The instruments used to measure neurological and neurobehavioral outcomes for this study were selected to fulfill the following criteria:

- Sensitive to change after brain injury and over time
- Sensitive to multiple levels of outcome including impairment, activity, participation, and the quality of life of the child and family
- Sensitive to subtle differences in level of cognition, at both the mild and severe ends of the spectrum

These instruments are described below, and the overall schedule of assessments is provided in [Table 2 on the following page](#). While some instruments will also be used at hospital discharge and 3 months, all primary and secondary outcome measures will be based on 12-month measurements. Data collected at earlier time points will be used for exploratory analyses.

6.6.1 Vineland Adaptive Behavior Scale (VABS)

The Vineland Adaptive Behavior Scale (VABS) was designed as a caregiver report measure to assess communication, daily living, social, and motor domains of adaptive behavior.⁴⁵ It has basal and ceiling criteria that allow for focused evaluation of each child's skill level, resulting in typical administration time of only 30 minutes. Normative data are available on children from birth through 18 years of age. Based on the normative data, standardized scores can be calculated that allow comparison of the child's functional status to other children of similar age. Moreover, the VABS-II⁴⁶ was revised and validated with more emphasis on young children. Like the VABS, the VABS-II has normative data available for children from birth through 18 years of age. The VABS-II is a continuous measure derived from developmental data using either a semi-structured, caregiver interview, or caregiver report form. Unlike other caregiver report measures of adaptive behavior, such as the Scales of Independent Behavior-Revised⁴⁷ and the Adaptive Behavior Assessment Scale-Second Edition,⁴⁸ the VABS-II has only one version of the test for the age range of interest (0 to 18 years), whereas the other tests have different versions for children of varying ages. Therefore, the VABS-II allows better comparison throughout the entire age range of this study. Additionally, the VABS-II has more items that capture behaviors of very young or low functioning children as compared to the other two measures. This is particularly important in this sample of children where there is the potential for many of the older children to be low functioning.

Table 2: Schedule of Assessments for Neurobehavioral Outcomes and Related Measures

Measurement	Baseline	PICU Discharge	Hospital Discharge	Three months	Twelve months
Pre-existing medical conditions	X				
Pre-existing developmental disabilities	X				
Family and household information	X				
Family function (FAD)	X				
Severity indicators (I.e. trach, vent, tube fed)	X		X	X	X
Location (acute hospital, rehabilitation, SNF, home)	X		X	X	X
Global function questions	X			X	X
POPC/PCPC	X	X	X	X	X
VABS-II	X			X	X
Family burden (ITQOL/CHQ)	X			X	X
Neuropsychological testing (Mullen or WASI)					X
Neurological abnormality assessment					X

Inter-interviewer reliability was high for the overall Adaptive Behavior Composite (.87 for children ages birth through six and .74 for ages 7 through 18 years).⁴⁶ While the VABS-II was not specifically designed to assess outcome after neurological injury, several studies have found the VABS to be sensitive to severity of neurological injury.^{49, 50} Also, the VABS was used as a primary outcome in completed multicenter, randomized clinical trials in children with infantile spasms⁵¹ and in children with Fragile X Syndrome.⁵² It is currently being used as an outcome measure in several NIH funded clinical trials of pediatric patients with a variety of neurological disorders (clinicaltrials.gov). Deficits in functional skills, based on the VABS, have also been noted in several studies of children with cardiac arrest.^{49, 53} While the VABS-II is not able to measure subtle differences in skills in very low functioning children, this is true of all measures of neurobehavioral outcome, and compared to other comparable measures,^{47, 48} the VABS-II has a greater number of items to assess lower level skills.

Pre-cardiac arrest baseline information will be obtained with the caregiver rating form, and the 3 and 12 month VABS-II assessments will be obtained by interview. Agreement between the interview and caregiver rating form was found to be very high⁴⁶ and therefore the two methods can be compared directly.

Follow up interviews will be conducted by telephone. All follow up telephone interviews for VABS-II will be administered centrally by a trained clinician at the Kennedy Krieger Institute (Johns Hopkins School of Medicine, Baltimore, MD).

Telephone interviews, rather than in-person interviews were chosen for several reasons:

- The telephone interview allows for the administration of the VABS through a central site with expertise in outcome assessment. Administration at this central site will enable us to utilize select well trained professionals with direct ongoing oversight by a Psychologist (preferably a Ph.D. Neuropsychologist). This methodology is expected to decrease measurement variability and error.
- The telephone interview allows for increased participation rate for the primary outcome variable, as barriers to returning to a medical center are eliminated. This is especially relevant for those who are severely impaired and thus more challenging to transport. Systematic attrition of the more severely impaired could significantly impact the results of this study. Therefore, every provision is being made to ensure inclusion of these subjects in the primary outcome.

- The VABS is based solely on caregiver information and not on observation of the child, therefore direct observation of the child is not necessary for accurate completion of this measurement. Moreover, reliability between in-person caregiver interview and telephone caregiver interview is extremely high.⁵⁴
- Also, when the VABS was used as a primary outcome in a successfully completed multicenter clinical trial in children with infantile spasms,⁵¹ it was administered at one central site by telephone interview.

Although the primary outcome for this study is based on the VABS-II at 12 months post arrest, the baseline VABS-II score will be used to exclude those with a score less than 70 from analysis of the primary outcome. This approach will enable us to enroll a representative cohort of pediatric ICU patients and to take into account that functional decline may be difficult to quantify in subjects with severe pre-existing neurobehavioral deficits. However, change in VABS-II from baseline to 12 months follow up in survivors will be examined as a secondary outcome in all study subjects.

In order to assess interrater reliability of the VABS II telephone interviews, and prevent variance in ratings over time, the first 4 interviews and thereafter every 10th interview will be recorded for quality assurance. If there is less than 80% agreement on the scoring of the interview, the plan for the recordings will restart with the initial frequency (4 interview followed by every 10th interview). If there is a new interviewer, the frequency will also start with the initial frequency. Staff at KKI will listen to recordings and reconcile any discrepancies within 3 months of the interview. The recordings will be erased immediately after the review and adjudication. Recordings are to be stored in the same manner as all study related documents and will be destroyed as soon as quality assurance activities have taken place

6.6.2 PCPC/POPC

The Pediatric Cerebral Performance Category (PCPC) and the Pediatric Overall Performance Category (POPC) scales have been recommended for reporting outcome following cardiac arrest in children.¹¹ As a consequence, the PCPC and POPC have been used in all the major outcome studies of childhood cardiac arrest.^{16, 17, 19, 55, 56} The PCPC provides a rating of neurological functioning, whereas the POPC provides a rating of overall health.

Both the PCPC and POPC can be reliably rated pre and post arrest based on a brief conversation with the child's family or medical record re-

view. Both measures were designed for children who experience cardiac arrest and are applicable to children who do not survive, those who survive in a vegetative state, and those survivors who are unable to cooperate with neuropsychological testing. These instruments provide a simple measure of overall severity and are correlated with other more lengthy measures of outcome, including the VABS.⁵⁷ The limitations of the PCPC and POPC are that they do not have normative data for different age groups. Moreover, the PCPC and the POPC do not allow for detailed measurement of functioning or measurement of subtle changes in function or cognition. Therefore, these measures are included for descriptive purposes only, to enable comparisons with results of other studies that used these measures, and are not a primary or secondary outcome of the study.

6.6.3 Neuropsychological Testing

In children, duration of cardiac arrest⁴⁹ and of circulatory arrest during heart surgery⁵⁸ have been associated with lower performance on measures of overall cognitive ability. Additionally, anoxic brain injury often significantly impacts specific neuropsychological skills, including attention, memory, executive functioning, processing speed and motor functioning.^{59, 60} To more fully describe these cognitive outcomes and identify subtler but significant impairments, a brief battery of neuropsychological testing will be administered 12 to 16 months post arrest, by designated psychologists at each study site. Measures were chosen that are sensitive to brain injury, have adequate normative data for the age range, plus good reliability and validity. For all children 5 years 8 months or younger, the Mullen Scales of Early Learning will be employed at 12 months post arrest to obtain a measure of overall cognitive functioning. Since the Mullen only has available data through age 5 8/12th years, for children 5 9/12th through 5 11/12th years, testing will be delayed until they are six years old, which may be as late as 16 months post arrest.

For children 6 years of age or older neuropsychology testing will be administered if the child usually "follow instructions" (question 10, VABS-II Receptive Communication) or usually "point or gesture to indicate preference" (question 10, VABS-II Expressive Communication), or have higher level communication skills. For these children, the 2-subtest version (Vocabulary and Matrix Reasoning) of the Wechsler Abbreviate Scale of Intelligence will be administered to obtain a measure of general cognitive functioning (estimated full scale IQ score). In addition, a battery of specific neuropsychological measures to assess processing speed, attention, learning

and memory, executive functioning (ability to plan, organize, and engage in goal directed behavior), and visual motor functioning will be administered to these children

Processing Speed. Processing speed will be measured by coding on the Wechsler Intelligence Scale for Children-IV (WISC-IV) and digit symbol-coding on the Wechsler Adult Intelligence Scale Third Edition (WAIS-III). These are essentially the same task, but coding has normative data available for ages 6 through 16 and digit symbol has normative data available for ages 16 and older. In this study, the coding from the WAIS-III will be used for adolescents 17 years or older at the time of follow up. For this test, the individual copies symbols that are paired with simple geometric shapes or numbers. They use a key to draw the symbols in the correct boxes within a 2-minute time limit. This test is consistently more sensitive to brain damage than other Wechsler battery tests and it is the score that is most likely depressed even when damage is minimal.⁶¹ The test-retest reliability (range 0.67 to 0.81) and interscorer agreement (0.98-0.99) is also good for this test. Coding has been shown to be sensitive to even mild TBI.⁶¹

Attention. Attention will be measured using the Digit Span subtest from the Wechsler Intelligence Scale for Children-IV (WISC-IV) and the Wechsler Adult Intelligence Scale Third Edition (WAIS-III).⁶²⁻⁶⁴ Digit Span is a measure of auditory focused attention and working memory. Part one requires the subject to repeat strings of digits presented by the examiner. The strings are two to nine digits in length and are presented at the rate of one digit per second. For part 2, the examiner again presents increasingly longer strings of digits, but for these items the subject is required to reverse the order of the digits. On the WISC-IV, normative data for Digit Span are available for ages 6 through 16 years. For children 17 years and older at the time of follow up the WAIS-III Digit Span will be used. Research has indicated that digits forward span has been found to fall below normal limits in some patients following head injury, but it is also likely to show return to normal levels during subsequent years.^{65, 66} Digit Span backwards has also been shown to be sensitive to many types of brain damage.⁶¹ Digit Span demonstrates good test-retest reliability (0.81 for children and 0.75 for adults) and interscorer agreement (0.98-0.99).⁶²⁻⁶⁴ Previous research has found Digit Span backward to be sensitive to TBI.^{61, 65, 66}

Learning and Memory. The California Verbal Learning Test - Children's Edition (CVLT-C)⁶⁷ and the California Verbal Learning Test - Second Edition (CVLT-II)⁶⁸ are supraspan list-learning tasks, that will be used to measure verbal learning and memory. The CVLT-C is comprised of five recall trials of a 15-item word list; the list items belong to 3 semantic categories (Fruits, Clothing, Toys), whereas the CVLT-II is comprised of a list of 16 words in 4 semantic categories. For both tasks, there are five learning trials that followed by a single presentation of a distracter list, a second, novel word list. Learning and memory is assessed by number of words recalled over the 5 learning trials, after presentation of the distracter list (short-delay free and cued recall), after a longer 20-minute delay (long-delay free and cued recall), and on recognition. The CVLT-C has normative data available from ages 5 through 16 years, whereas the CVLT II has normative data available for ages 16 through adulthood. The CVLT-II will only be used in this study for adolescents 17 years of age or older at the time of follow up. According to the standardization manuals, the CVLT-C and CVLT-II have moderate to high internal consistency. In contrast, test-retest variability is variable, with improvement noted during the second administration due to learning effects. Moreover, the CVLT-C and CVLT-II have been associated with severity of brain injury.⁶⁸⁻⁷⁰

To measure visual memory, Rey Osterrieth Complex Figure (ROCF)^{71, 72} will be employed. This task involves the child drawing a complex geometric figure from memory, after copying the figure. A standardized scoring system will be used to measure the accuracy of the recalled figure based on the overall shape and details of the figure. There is a short delay (approximately 3 minutes) and long delay (approximately 30 minute) recall trial. Additionally, after the 30-minute delay trial, there is a recognition trial in which the child will be asked to choose the correct details. The ROCF will be scored using the Meyers and Meyers Scoring System, which includes normative data for ages 5 years and older.^{73, 74} The test has good inter-rater reliability (0.93 to 0.99).⁷³ Meyers and Lange found that brain injured adults performed significantly worse on the ROCF (immediate and delayed recall) compared to psychiatric patients and normal controls.⁷⁵

Executive Functioning. We will measure rapid generation of verbal information using the Controlled Oral Word Association Test (COWA).⁷⁶ This test requires the individual to generate words that begin with a particular letter as quickly as possible during a one minute trial. Normative data are available for children ages 6 to 13⁷⁷ and then 15 to 20 years.⁷⁸ For chil-

dren, aged 14 at the time of the evaluation, the normative data for the next youngest group will be used. Test-retest reliability for the COWA is good.⁷⁹ Several studies have found the COWA to be highly sensitive among persons with brain injury.⁸⁰⁻⁸²

In addition to using the ROCF to measure visual memory (as above), we will use the ROCF copy trial to measure executive functions.⁷¹⁻⁷⁴ For this task, the child will be asked to copy a complex geometric figure, while the figure is directly in front of the child. A standardized scoring system will be used to measure the accuracy of the copy based on the overall shape and details of the figure. Normative data are available on this measure from age 5 to adulthood. Additionally, test retest reliability and interrater reliability were adequate.^{73, 74} The ROCF correlates highly with other measures of visuoconstructional ability.^{83, 84} Moreover, the copy of the ROCF has been found to be sensitive to the sequelae of brain injury in children.⁸⁵

Visual-Motor Functioning. To measure fine motor dexterity bilaterally, the Grooved Pegboard Test⁸⁶ will be administered. This task requires the child to insert pegs into shaped holes on a board. Normative data are available for ages 5 and older.⁸⁷ For ages 5 through 8, children are only required to complete two rows of pegs. For older children, all rows are completed.

The Beery Buktenica Developmental Test of Visual-Motor Integration-Fifth Edition (VMI)⁸⁸ will be employed to assess ability of children to copy geometric figures of increasing complexity. Normative data are available for ages 2 through 18 years. The 18 year old normative data will be used to calculate standard scores for any individual 19 years of age at the time of the follow up evaluation. Overall odd-even internal consistency is adequate (.88). Inter-scorer reliability is also high (.92). The VMI correlates moderately with overall intellectual abilities. Also, children with neurodevelopmental disabilities associated with low birth weight and spina bifida perform poorly on the VMI compared to typically developing peers.^{89, 90}

These measures are summarized in Table 3 on page 44.

6.6.4 Neurological Abnormality Assessment

A detailed standardized neurological exam will be performed in all 12 month survivors by a pediatric neurologist at each site. In order to compare outcomes between groups, and to take into account the different number of exam elements that can be evaluated among survivors of different ages and functional levels, two age-related systematic quantitative scoring systems have

been devised. The scoring systems, Pediatric Resuscitation after Cardiac Arrest (PRCA1 for up to age 3 and PRCA2 for age 3 and older), are derived from the Pediatric Stroke Outcome Measure (PSOM) stroke scale, which is already being used successfully in a multi-center pediatric study of outcome after stroke (in children with sickle cell disease) (ref UO1-NS 042804). Since it is possible that the range in severity of deficits will be greater in the THAPCA study population than in pediatric stroke survivors, the PRCA1 and PRCA2 have an expanded scoring system. All elements of the evaluation represent integral components of age-appropriate neurological evaluation of children. These components include level of consciousness, behavior and mental status, language, cranial nerves, and motor skills. In addition to descriptive material, each exam generates two scores: a global assessment score (0-21 point range), and a normalized cumulative abnormality score.

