4.3 Secondary Endpoints

Secondary endpoints of each THAPCA trial are:

1. Survival at 12 months post cardiac arrest;
2. Change in neurobehavioral function from pre-cardiac arrest baseline to 12 month measurement (VABS II);

For survivors only,

3. Neuropsychological scores at 12 month evaluation;
4. Neurological abnormality scores at 12 month evaluation.

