6.1 Screening, Enrollment, and Randomization

Clinical investigators in each site will be pediatric critical care or emergency medicine specialists; in many sites, there will be an assigned investigator in the intensive care unit and in the emergency department. The THAPCA-OH (out-of-hospital) Trial will be enhanced by close cooperation between specialists in the emergency medicine and critical care.

For cardiac arrest cases occurring in the in-hospital (IH) setting, screening will be straightforward. The assigned study physician will be notified by the clinical team as soon as possible after the ROSC/ROC occurs. In the out-of-hospital (OH) setting, the emergency medicine (EM) staff will similarly notify the assigned study physician who performs screening of cases of any arrests occurring in or coming to the emergency department. In the event of a case at another facility, the PICU or EM clinical team arranging the transport will notify the study physician for screening.

The assigned study physician will screen/review each patient for potential eligibility. A screening log will be completed for all CA patients, whether eligible or not eligible. If a patient meets inclusion/exclusion criteria for study participation, the subject's parent(s)/guardian(s) will be approached for written informed permission for the child to participate in the appropriate THAPCA trial (see Section 10.2 on page 66). Following written permission, patients will be randomized to hypothermia treatment or normothermia control therapy. Patients must be randomized within six hours of ROSC/ROC.

Note: Pregnancy is a contraindication for participation in this study. All female patients of child-bearing potential must have a negative urine or blood pregnancy test prior to enrollment.

Randomization for each trial will be stratified by clinical center and patient age group (less than 2 years, 2 to 11 years, 12 years or older). The DCC will prepare randomization schedules using randomized blocks of varying length for each of these study strata. Patients within each stratum will be randomized in a 1:1 ratio to hypothermia or normothermia. Patient randomization will be accomplished using either an Internet connection to the DCC, or an interactive telephone service.

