8.6 Three Month Follow Up

Caregivers will be contacted at three months post arrest and will be asked the status of the patient, location of the patient, and if the patient has undergone any additional procedures or therapies. The caregiver will be asked to provide information on family burden, the patient's global function, POPC, and PCPC. The VABS-II assessment will be done at this time. If the respondent is the child's treating healthcare professional the information on family burden will not be collected. All telephone follow up at three months will be conducted centrally by staff at the Kennedy Krieger institute (Johns Hopkins School of Medicine, Baltimore, MD) to assure uniform performance of the VABS-II assessment. In order to assess interrater reliability of the VABS II telephone interviews, and prevent variance in ratings over time, a subset of interviews (every 10th interview) will be recorded. Recorded interviews will be reviewed and rescored by [name]. Discrepant scores will be adjudicated through discussion between [name] and the psychometrician.

The three month follow up has several purposes. First, the contact will help with subject retention by maintaining communication with the family. Second, the three month assessment will be used to test our primary endpoint conclusions for robustness with respect to missing data (see Section 9.2 on Page 59). Third, it is of exploratory interest to determine if there is a trajectory of improvement between three months and 12 months.

8.7 12 Month Follow Up

Parents will be contacted at 12 to 16 months post arrest and will be asked the status of the patient, location of the patient, and if the patient has undergone any additional procedures or therapies. The parents will be asked to provide information on family burden, the patient's global function, POPC, PCPC, and VABS-II assessment. In addition to measures administered over

the phone, the patient will have a neuropsychological evaluation and neurological assessment performed at the study site at 12 to 16 months post arrest.

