The neurological abnormality scores will be measured as continuous outcomes for those who complete the exam. Comparison between the study groups will employ a two-sample t-test if appropriate, or alternatively, the Wilcoxon rank-sum test if basic normality assumptions are not met.

Narrative descriptors for each element of the PRCA (Section 6.6.4 on page 43) will also be analyzed by study investigators to characterize patterns of neurological dysfunction in survivors (e.g. specific movement disorders or

cognitive deficits).

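### The neurological abnormality comparison in Protocol 9.3 could be stratified by PRCA version at almost no cost: survivors are scored on two age-specific instruments but compared with a single unstratified test

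*Protocol*

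**What the plan says.** Protocol 6.6.4 sets up two scoring systems, "Pediatric Resuscitation after Cardiac Arrest (PRCA1 for up to age 3 and PRCA2 for age 3 and older", and gives as a reason the need "to take into account the different number of exam elements that can be evaluated among survivors of different ages and functional levels". It adds that "each exam generates two scores: a global assessment score (0-21 point range), and a normalized cumulative abnormality score".

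Protocol 4.3 lists "Neurological abnormality scores at 12 month evaluation" as the fourth secondary endpoint, for survivors only. Protocol 9.3 gives its analysis: "The neurological abnormality scores will be measured as continuous outcomes for those who complete the exam", and then "Comparison between the study groups will employ a two-sample t-test if appropriate, or alternatively, the Wilcoxon rank-sum test" if normality does not hold. No stratum or covariate for instrument or age is named.

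Two design features bear on this. Randomization (Protocol 6.1) is "stratified by clinical center and patient age group (less than 2 years, 2 to 11 years, 12 years or older". Protocol 8.7 has the "neurological assessment performed at the study site at 12 to 16 months post arrest".

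**The concern.** Protocol 9.3 does not say in so many words that PRCA1 and PRCA2 results are combined, but that is the natural reading. In the paragraph just before, the same section keeps the Mullen scales for younger children apart from the battery for those aged 6 and over. It makes no such split for the neurological scores.

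Normalization adjusts for how many elements could be examined. It does not by itself give two instruments the same mean or spread in children with equal neurological status, and nor does a shared 0-21 range. If an offset remains, a test that ignores the instrument counts it as unexplained variation and loses power in a survivor-only sample that is already reduced. If the mix of instruments also differed between arms, part of the offset would appear as a treatment difference.

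**Working it through.** The protocol states no SD, effect size or power for this endpoint, so there is no figure of its own to reproduce. The size of the effect has to be worked out under assumptions.

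**Inputs.**
- From the documents: two-sided alpha 0.05 (9.1); enrollment of 300-350 out-of-hospital and 450-600 in-hospital (5.6); survival to discharge of 28% of live out-of-hospital admissions and 236/459 = 51% in-hospital after return of circulation (2.3.2).
- Assumed: d, the offset between instruments in within-instrument SDs (0.25, 0.5, 1.0); w, the PRCA1 share of survivors (0.3-0.7); survival to discharge as a stand-in for 12-month survival.
- Implied survivors: 0.28 × 300 = 84 to 0.28 × 350 = 98 out-of-hospital; 0.514 × 450 = 231 to 0.514 × 600 = 309 in-hospital.

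**Power.** With within-instrument SD 1, the pooled SD is √(1 + w(1−w)d²). Take an effect that gives a stratified test 80% power, so that effect/SE = 1.960 + 0.842 = 2.802. The unstratified power is then Φ(2.802/SD − 1.960), which does not depend on the number of survivors. At w = 0.5:

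| d | pooled SD | unstratified power | equivalent loss of survivors, 1 − 1/SD² |
|---|---|---|---|
| 0 | 1.000 | 80% | 0% |
| 0.25 | 1.008 | 79.4% | 1.5% |
| 0.5 | 1.031 | 77.6% | 6% |
| 1.0 | 1.118 | 70.7% | 20% |

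At w = 0.3 or 0.7 the powers are 79.5%, 78.0% and 72.1%.

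This formula lets the mix vary by chance. If it were exactly equal in the two arms, only the estimated SD would be inflated, and power would be Φ(2.802 − 1.960 × SD): 79.6%, 78.3% and 72.9% at w = 0.5. The order of magnitude is the same.

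**Balance by design.** A child under 2 at arrest is under 3 at exactly 12 months, and a child of 2 or more is at least 3. The age-2 stratum cut therefore nearly predicts the PRCA version. The exception is children aged 20 months (36 − 16) to under 24 months at arrest, who may turn 3 before an exam held as late as 16 months.

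**Type I error with a balanced mix.** The unstratified t-test is conservative. In 20,000 simulated trials with w = 0.5 and d = 0.25, 0.5 and 1.0, it rejected in 4.8%, 4.3% and 2.7% at 45 per arm, and in 4.9%, 4.4% and 3.0% at 135 per arm.

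**Bias if the mix shifts.** Suppose hypothermia raised survival by g only in the younger children, from a base s. The PRCA1 share in that arm becomes w(s+g)/[w(s+g) + (1−w)s].
- s = 0.28, w = 0.5, g = 0.10: 0.38/0.66 = 0.576, a shift of 0.076. With g = 0.15: 0.43/0.71 = 0.606, a shift of 0.106.
- s = 0.51, w = 0.5: 0.61/1.12 = 0.545 and 0.66/1.17 = 0.564, shifts of 0.045 and 0.064.
- Over w = 0.3-0.7 the shift is 0.04-0.11. Spurious difference = d × shift: 0.01-0.03 SD at d = 0.25, 0.02-0.05 SD at d = 0.5, 0.04-0.11 SD at d = 1.0.

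With a 0.08 shift, simulated type I error is 4.8%, 5.4% and 6.3% at 45 per arm, and 5.4%, 6.1% and 9.0% at 135 per arm (d = 0.25, 0.5, 1.0).

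**The case against.** The strongest reply is that the offset is assumed. Both versions derive from the same stroke scale, 6.6.4 gives one list of components for the examination, and the two scores were built to allow comparison across ages. With no offset nothing is lost. This stands: the protocol shows no offset. But it also reports no equating that would rule one out, and stratifying costs almost nothing either way.

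A second reply is that pooling is inferred and that a stratum for a secondary endpoint may be left to the analysis plan. That is fair, and if the plan already stratifies, the point is met. The protocol does name the test, however, and the test it names has no stratum.

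A third is that age-stratified randomization already balances the instruments. It largely does, among those randomized. The analysed set is survivors who complete the exam, so balance there is likely but not guaranteed. Even perfect balance leaves the loss of power.

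A reader might go further and infer that the comparison is biased, with type I error of 9-20% in the in-hospital trial. That range comes from assuming that PRCA1 makes up 45% of survivors in one arm and 60% in the other, with offsets of 0.5-1.0 SD. The odds ratio of that mix is (0.60/0.40)/(0.45/0.55) = 1.83. If only younger children benefited, their survival would have to rise from 28% to about 51%, or from 51% to about 93%. Nothing in the protocol supports a contrast of that size. An instrument term would also not cure the survivor selection that such an effect would bring, nor would it remove age differences within PRCA2, which runs from age 3 through adolescence.

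**Conclusion.** This is a free improvement to a secondary endpoint, not a demonstrated error. Two age-specific instruments feed one unstratified comparison, and stratifying recovers whatever precision an offset would cost: about half a point of power at 0.25 SD, about 2 points at 0.5 SD and about 9 at 1.0 SD, from 80%, and nothing at zero. The offsets and the PRCA1 share are assumptions; the protocol gives neither.

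Bias is secondary. It requires an offset together with an age-dependent effect on survival or exam completion, and it stays small unless the offset is large. With a balanced mix the planned test is conservative, so the documents do not support a claim that it is invalid. The primary endpoint, its power tables and the safety endpoints are unaffected.

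**What to change.** In Protocol 9.3, replace the two-sample comparison of neurological abnormality scores with a linear model containing treatment and PRCA version. If normality fails, use the van Elteren (stratified Wilcoxon) test with version as the stratum. Report the treatment effect by version descriptively.

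The randomization age stratum may be used in place of version. It is fixed at baseline, whereas version can depend on the exam date for children just under 2 at arrest.

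The cost is one sentence and about one degree of freedom. No new data are needed, because version follows from age at the exam.
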